### 3.2.3. EQ-5D-5L

Developed by the EuroQoL Group, the EQ-5D-5L (EuroQoL, 5 dimensions, 5 levels) is considered the premier measure of health status used in the assessment of the Quality Adjusted Life Year. It measures 5 dimensions of health on a 5-point scale including mobility, self-care, usual activities, pain/discomfort, and anxiety/depression.

Also included is a visual analog scale (VAS) anchored by worst and best imaginable health on a 0 to 100 scale where participants are asked to indicate where on the scale they rate their current health.

Missing data will not be imputed, which means missing individual question responses will lead to missing dimension scores and Index (total) score. EQ-5D-5L baseline is the latest evaluation prior to PF-07055480 infusion.

Each of the 5 dimensions (ie, ‘Mobility’, ‘Self-care’, ‘Usual activities’, ‘Pain/discomfort’, and ‘Anxiety/depression’) in the EQ-5D-5L questionnaire is assessed with 5 levels of perceived problems:

Level	Description	Score
Level 1	No problem	1
Level 2	Slight problems	2
Level 3	Moderate problems	3

---

Level 4	Severe problems	4
Level 5	Extreme problems	5

A health state is defined by the combination of one level from each of the 5 dimensions. There is a total of 3125 possible health states. For example, state 11111 indicates no problems on any of the 5 dimensions, while state 12345 indicates no problem with mobility, slight problems with washing or dressing, moderate problems with doing usual activities, severe pain or discomfort and extreme anxiety or depression.

The Index score (total score) of EQ-5D-5L will be obtained, according to the health state defined by the 5 dimension scores, from the Crosswalk Index value calculator and table lookup document under the target country population. For the clinical study report, weights under the US population will be used to obtain the Index score.

### 3.2.4. FVIII Inhibitor

FVIII inhibitor assessments will be collected according to protocol-specified SoA. Results provided by the central laboratory as <0.6 Bethesda units (BU) will be considered as negative.

### 3.2.5. Vector Shedding

Samples of plasma, saliva, urine, stool, and semen will be collected as specified in the protocol SoA for analysis of vector shedding. Peak values, time to peak value, time to undetectable/negative vector (defined as time to first of 3 consecutive specimens under the limit of detection), time to last of 3 consecutive negative results, and time to last positive result prior to 3 consecutive negative results will be derived for each specimen type. A result indicating it is below the lower limit of quantification will be shown in the listing as reported and will be set as 1 for plotting purposes.

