8.5. Pharmacokinetics

8.5.1. AAV2/6 Vector Shedding

AAV2/6 genome in plasma, saliva, urine, stool, and semen by polymerase chain reaction (PCR) will be assessed as described in the SoA ([Table 1](#)). On Day 0, vector genome titer should be obtained in plasma only at 12 hours from the start of the infusion \pm 1 hour.

After Week 12, collection will only continue until three consecutive negative samples are obtained on a sample-type basis (Weeks 16, 20, 24, 28, 32, 36, 40, 44, 48, and 52 [\pm 1 week] and every 1 month after Week 52 to Month 60 [\pm 1 month]). For example, after urine sample results are negative 3 consecutive times, the urine sample will stop being collected while the other samples may continue to be collected if they continue to be positive.

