### **5.2.3. Analyses for Continuous Endpoints**

Summary descriptive statistics for continuous variables will include the number of observations with non-missing values, mean, standard deviation, median, first quartile, third quartile, minimum, and maximum values.

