## **5.3. Methods to Manage Missing Data**

In general, missing data will not be imputed in this study, unless specified in [Section 3](#), where individual endpoints are discussed.

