### 6.2.5. Vector Shedding

The peak value, time to peak value, and time to undetectable/negative vector (first of 3 consecutive negative results), time to last of 3 consecutive negative results, and time to last positive result prior to 3 consecutive negative results will be summarized by specimen type, stratified by dose level. Number and percentage of participants who achieved 3 consecutive negative results will be reported for each specimen. Peak value information and time to undetectable/negative vector will also be presented in a data listing. Vector genome values for each study visit will be listed by specimen type. Individual profile plots of vector genome values over time (log scale) will be presented by dose level for each specimen type.

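### The vector clearance times have no censoring rule, so under the SAP's default rules participants without 3 consecutive negatives drop out of the summaries and shedding duration is understated on average

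*SAP*

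**What the plan says.** SAP 3.2.5 derives three durations for each specimen type. The first is "time to undetectable/negative vector (defined as time to first of 3 consecutive specimens under the limit of detection". The second runs to the last of those 3 negatives, and the third to the last positive before them.

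SAP 6.2.5 says how they are reported. The peak value, the time to peak and all three durations share one sentence, which ends "time to last positive result prior to 3 consecutive negative results will be summarized by specimen type, stratified by dose level". It names no estimator, no censoring rule and no value for a participant who has not reached 3 negatives.

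The general rules then apply. SAP 5.2.3 reads "Summary descriptive statistics for continuous variables will include the number of observations with non-missing values, mean, standard deviation, median" and continues with quartiles and range. SAP 5.3 reads "In general, missing data will not be imputed in this study", unless Section 3 specifies otherwise. For these durations SAP 3.2.5 specifies nothing. Its one rule for substituting a value concerns plotting results below the limit of quantification.

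Three other provisions bear on the point:

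- SAP 6.2.5: "Number and percentage of participants who achieved 3 consecutive negative results will be reported for each specimen".
- SAP 6.2.5: "Individual profile plots of vector genome values over time (log scale) will be presented by dose level for each specimen type", plus listings of visit values, peak values and time to undetectable vector.
- Protocol 8.5.1: "After Week 12, collection will only continue until three consecutive negative samples are obtained on a sample-type basis". Samples are 4-weekly from Week 16 to Week 52, then monthly to Month 60.

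**The concern.** These are right-censored durations. A participant may lack 3 consecutive negatives because he is still positive, because he has only 1 or 2 negatives so far, or because he left before clearing. In each case his duration is known only to exceed some value. Leaving him out makes the summary conditional on having cleared within the observed follow-up, which favours short times.

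Vector shedding is a secondary endpoint (Protocol Section 3), and Protocol 9.4.1 also lists it among the descriptive analyses supporting the primary safety endpoint. About 20 participants over the four cohorts in SAP 6.5.3 is 5 per cohort on average, so one or two omitted participants can shift a cohort's mean or median. SAP 7.1 plans an interim analysis one year after the last infusion and allows others for health authority interactions. Late-dosed participants have the least follow-up at such cuts.

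**Working it through.** The plan states no clearance time, event count or precision target, so there is no figure to reproduce. The check has three parts. All clearance times below are assumed, because the documents give none.

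**1. Does the text lead to a cleared-only summary?** The durations exist only after 3 negatives (SAP 3.2.5). They are summarised without a stated method (SAP 6.2.5). Continuous summaries use non-missing values (SAP 5.2.3), and missing values are not imputed (SAP 5.3). Together these give a summary of clearers only. This is an inference from four sections; no single sentence says it.

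**2. Small cohorts by hand, five participants each.**

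- *Two uncleared.* Three clear at Weeks 12, 16 and 20, and two are still positive at Week 52. The cleared-only median is 16 weeks (n = 3). Kaplan-Meier gives S(12) = 4/5 = 0.8, S(16) = 3/5 = 0.6 and S(20) = 2/5 = 0.4, so the median is 20 weeks.
- *Three uncleared.* The curve stops at 3/5 = 0.6 and the median is not reached. The cleared-only summary would still print one.
- *One uncleared.* Four clear at Weeks 8, 12, 16 and 20, and one is positive at Week 52. The cleared-only mean is 56/4 = 14.0 and the median is 14.0. With all five, the median is 16 and the mean is at least (56 + 52)/5 = 21.6.
- *An early leaver.* Four clear at Weeks 12, 16, 20 and 24. The fifth leaves at Week 4 and would have cleared at Week 8. The cleared-only mean is 72/4 = 18, while the true mean is 80/5 = 16. Here the summary overstates.

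**3. Simulation of time to first of 3 negatives.** Samples were at Weeks 1, 2, 4, 8 and 12, 4-weekly to Week 52, then monthly to Month 60 (Protocol Table 1 and 8.5.1). Assumptions: lognormal clearance with median 8, 16 or 32 weeks and log-SD 0.8; exponential dropout at about 0, 5 or 20% per year; 1,500 trials per scenario. Mean weeks for n = 20, cleared-only against true:

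| Assumed median | Week 52 cut, negligible dropout | Week 260 cut, 5% per year | Week 260 cut, 20% per year |
|---|---|---|---|
| 8 | 12.1 v 13.0 (98% clear) | 12.9 v 13.0 (98%) | 12.6 v 13.0 (92%) |
| 16 | 18.6 v 23.9 (90%) | 23.6 v 24.0 (97%) | 22.5 v 24.0 (88%) |
| 32 | 25.1 v 44.7 (66%) | 43.3 v 44.7 (95%) | 40.1 v 44.5 (82%) |

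With n = 5 the Week 52 means were similar: 12.0 v 12.9, 18.7 v 24.2 and 25.4 v 44.8.

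In the slowest Week 52 scenario (n = 20), the typical cleared-only median was 24 weeks, against 34 true and 32 by Kaplan-Meier. The Kaplan-Meier median was read as the first time the curve reached 0.5 or below.

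Averaged over trials, the cleared-only mean was at or below the true mean in every scenario. In single trials with at least one non-clearer, it exceeded the true mean in 0% with a Week 52 cut and negligible dropout. With a Week 260 cut and 5 to 20% dropout per year it did so in about 18 to 45%.

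**The case against.** The best defence is that this is an unstated detail in a purely descriptive analysis whose design largely contains the problem. Each specimen type is sampled until 3 negatives or Month 60. At full follow-up with 5% dropout per year, the simulated gap is at most 44.65 − 43.31 = 1.34 weeks, less than one 4-week sampling interval. The number and percentage cleared, the profile plots and the listings make every non-clearer visible among about 20 participants. SAP 7.2 does not name shedding among its possible interim outputs, although its list is open and includes safety. All of this stands and limits the importance of the point. It does not change the tabulated mean or median, which remain conditional on clearing.

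A reader might also infer more than the documents support:

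- *That the SAP states a cleared-only method.* It does not; its default rules lead there.
- *That duration is understated whenever someone is uncleared or leaves early, or that each omitted participant is the longest shedder.* Leaving after clearance has no effect, and the early-leaver example goes the other way.
- *That participants' contraception would be affected.* Protocol 5.1 and Appendix 4 tie contraception to each man's own semen results and a minimum period. No cohort summary enters that rule.
- *That the highest dose cohort is affected most.* The documents give no clearance times by dose.

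**Conclusion.** The point holds as a minor one. The SAP has no censoring rule for durations that exist only after 3 consecutive negatives, and its own defaults remove everyone else, which biases the summaries downward on average.

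The size depends on how many are uncleared at the cut. Under the assumed distributions, the mean at a Week 52 cut falls short by about 1 week with 98% cleared, 5 weeks with 90% and 20 weeks with 66%. With follow-up to Week 260, the shortfall is up to about 1.3 weeks at 5% dropout per year and about 4.4 weeks (44.51 − 40.09) at 20%. If everyone clears before the cut there is none. These figures show direction and scale only; they do not predict this trial's results.

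**What to change.** In SAP 6.2.5, for each specimen type, summarise the clearance times by Kaplan-Meier. Give the median and range, mark censored values, and print not reached where that applies. Put the number cleared out of the number sampled beside each summary. Where a cohort is very small, pool dose levels or simply list the values.

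The censoring time has to differ by variable:

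- *Time to last of 3 negatives:* censor at the last sample.
- *Time to first of 3 negatives:* censor at the last positive sample, or at the first negative of an incomplete trailing run. Do not use the last sample. A participant positive at Week 44 and negative at Weeks 48 and 52, with a cut at Week 52, would be recorded as uncleared to Week 52, yet a third negative would date his clearance to Week 48.
- *Time to last positive:* censor at the last observed positive.

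The cost is a short paragraph in the SAP, a censoring flag in the dataset and a changed table. The downside is that Kaplan-Meier estimates are imprecise in cohorts of a few participants. If everyone clears, the curve is the ordinary empirical distribution and nothing is lost. No data collection, sample size or error rate is affected.

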## 3.3. Exploratory Endpoints

### 3.3.1. FVIII Antigen

Blood samples will be collected as specified in the SoA of the protocol and as specified in the Laboratory Manual to measure FVIII antigen levels. Results reported as BLoQ will be set as 0.009 IU/mL (0.9%) for analysis purposes. Any sample taken within 96 hours after administering exogenous FVIII replacement therapy will be excluded from summaries and analysis. In addition, FVIII antigen data collected after a participant initiates or resumes a prophylaxis regimen will be excluded.

### 3.3.2. Immunogenicity

The following immunogenicity assessments (listed in the table of protocol-required safety laboratory assessments) will be performed over time and reported:

- Total and neutralizing antibodies to AAV2/6 (anti-drug antibodies [ADA] and neutralizing antibodies [nAb]):

- For nAb (test MRD10), numerical values  $\geq 0.34$  will be considered as ‘negative’ and numerical values  $<0.34$  will be considered as ‘positive’.
- Cellular responses against FVIII and AAV (ELISPOT assay);
- Measurements of C-reactive protein (CRP) and interleukin-6 (IL-6).

### 3.3.3. Von Willebrand Factor

Blood samples will be collected, prepared, and stored as specified in the SoA of the protocol and in the Laboratory Manual.

### 3.3.4. GAL3BP and sEGFR

Expression of both soluble epidermal growth factor receptor (sEGFR) and galectin-3-binding protein (Gal3BP) will be measured at baseline in serum samples.

### 3.3.5. FVIII Steady State

Due to the small sample size and high inter-subject variability of PF-07055480 transgene expression, including FVIII activity levels, both mean and median values of FVIII levels using chromogenic and one-stage assays will be presented for each visit to assist in determining the onset of steady state of transgene expression.

### 3.3.6. Optional Liver Biopsy Substudy

An optional liver biopsy can be performed (in participants who consent to do so and as per investigator’s judgement) during the post-infusion period until year 5, ie, the end of the study. The procedure may be repeated once, later in the study, to assess evolution over time (in participants who consent to do so and as per investigator’s judgement).

This substudy may be proposed to any participant, unless there is a condition that, in the opinion of the investigator or a hepatologist or radiologist, would make liver biopsy contraindicated.

The exploratory objectives of the substudy are to evaluate vector integration in the liver, the histopathology of the liver tissue and to assess the expression of protein and/or RNA levels of FVIII and other biomarkers of interest in the liver (depending on collected material). A biopsy will be made upon investigator’s decision; it can be performed at any time post-infusion to assess liver health, integration and FVIII in the liver, but could also be triggered by sustained elevated FVIII activity levels, by a significant FVIII activity decline, by a sustained ALT elevation  $>$  ULN or to assess the long-term gene therapy effects on the liver.

## 3.4. Baseline Variables

Demographics, medical history, and hemophilia history will be collected at screening visit.

Baseline variables include age, race, ethnicity, sex, weight, height, body mass index (BMI), and 12-lead ECG. Age (years) at informed consent will be calculated as the integer part of (date of informed consent – date of birth)/365.25. For sites where only year of birth is

collected, age will be calculated as (year of informed consent from dosing study – year of birth). Age will be summarized as a continuous variable. BMI will be calculated as [(weight in kg)/(height in centimeters [cm])]\*10000.

### **3.5. Safety Endpoints**

#### **3.5.1. Adverse Events**

All adverse events will be coded using the most recent version of Medical Dictionary for Regulatory Activities (MedDRA) in place at the time of data cut or data base release. AE severity will be captured using common terminology criteria for adverse events (CTCAE; version 4.03) grading. An AE will be considered a treatment-emergent adverse event (TEAE) if the event started during or after PF-07055480 infusion, or on the day of PF-07055480 infusion if the time of the AE was not collected. AEs will be assessed throughout the study as described in the SoA, and at the early termination visit, if applicable.

In addition to reporting AEs across the entire study, the five yearly windows defined in [Section 5.2](#) will be used for AE reporting.

#### **3.5.2. Laboratory Data**

The safety and efficacy laboratory tests to be performed are provided in Protocol Appendix 2. Baseline will be defined as the last pre-infusion measurement.

#### **3.5.3. Vital Signs**

Vital sign measurements will include systolic and diastolic blood pressure (SBP and DBP), heart rate, respiratory rate, and temperature and will be measured during the complete physical examination. Additional measurements will occur on “Day 0” visit and “Day 1” visit. On the infusion day (“Day 0” visit) and the “Day 1” visit, vital signs will be obtained prior to infusion and then within 5 minutes of the start of the infusion, every 15 ( $\pm 5$ ) minutes for the length of the infusion, every 15 ( $\pm 5$ ) minutes until stable ( $\pm 10$  millimeters of mercury [mmHg]), then every 30 ( $\pm 5$ ) minutes until 2 hours post-infusions, then every 4 hours ( $\pm 10$  minutes) until discharge.

Baseline will be defined as the last pre-infusion recording.

#### **3.5.4. Electrocardiogram**

Standard 12-lead ECGs will be performed according to SoA.

#### **3.5.5. Physical Exam**

A complete physical examination will include, at a minimum, assessments of the cardiovascular, respiratory, gastrointestinal, and neurological systems. Height (cm) will be collected at screening only, and weight (kg) will be collected at screening and baseline only.

#### **3.5.6. Other Safety Parameters**

Chest X-ray, liver elastography, liver magnetic resonance imaging (MRI) and abdominal examination will be performed according to protocol.

## 4. ANALYSIS SETS (POPULATIONS FOR ANALYSIS)

Population	Description
Enrolled	All participants who sign the informed consent form (ICF) and meet all inclusion/exclusion criteria.
Safety	All participants enrolled in this study who receive any portion of study intervention.
Evaluable	All participants enrolled in the study who receive study intervention and have no significant interruptions of efficacy measurements.

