5.4. Screen Failures

Screen failures are defined as participants who consent to participate in the clinical study but are not subsequently entered in the study. A minimal set of screen failure information is required to ensure transparent reporting of screen failure participants to meet the Consolidated Standards of Reporting Trials (CONSORT) publishing requirements and to respond to queries from regulatory authorities. Minimal information includes demography, screen failure details, eligibility criteria, and any SAE.

Individuals who do not meet the criteria for participation in this study (screen failure) may be rescreened. Rescreened participants are required to sign a new ICF and will be assigned a different participant number.

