9.3. Analysis Set

For purposes of analysis, the following populations are defined:

Population	Description
Enrolled	All participants who sign the ICF and meet all inclusion/exclusion criteria.
Safety	All participants enrolled in this study who receive any portion of study drug and have at least one post-baseline safety assessment will be included in the safety population. All participants who enrolled in the study and received the study intervention.
Evaluatable	All participants enrolled in the study and take the full dose of study intervention and no significant interruption of efficacy measurement.

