		
Section 3.2.2, ABR:
 
Added “Total” (treated+untreated) ABR calculation for post-study drug infusion.
 
Removed version of post-study drug infusion ABR which does NOT exclude any days after routine prophylaxis is resumed.
 
Sections 3.2.3 and 6.2.3, EQ-5D-5L:
 
Information on EQ-5D-5L Index score was added.
 
Sections 3.2.5 and 6.2.5, Vector Shedding:
 
For vector shedding analyses, removed ‘overall’ (across specimen types), and added the summary of time to peak value.
 
Section 3.5.1, Adverse Events:
 
Treatment-emergent adverse event (TEAE) definition changed to Pfizer’s standard that became effective May 2019: “An adverse event will now be considered a TEAE if the event started during the effective duration of treatment.”
 
Section 4, Analysis Sets:
 
The populations for analyses were revised. “Intent-To-Treat” population was removed since this population is the same as the Safety population (Safety is now considered primary). “Enrolled” analysis set was added. And “Per Protocol” was changed to “Evaluable” with modifications. Removed, “and have at least one post-baseline safety assessment” from the definition of the Safety population that is given in the protocol amendment 4. The Safety population will be all participants who received study intervention.
 
Section 5.3.1, COVID-19 Considerations: Added analyses to assess the impact of COVID-19.
 
Section 5.2.1.1:

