### **6.5.2. Study Conduct and Participant Disposition**

The number of screened participants will be summarized. For screen failures, the reason for screen failure will be summarized using counts and percentages. No stratification by dose level will be implemented for this analysis. Enrolled participants are those who have been screened, are not considered to be a screen failure, and who have been approved by the Medical Monitor. A participant will be considered to have completed the study if he has completed all phases of the study including the End-of-Study visit (Month 60).

The number of participants enrolled, completing the study, discontinuing from the study and the primary reason for discontinuation, and the number of deaths (if any), will be summarized (number and percentage of enrolled participants in each population used for analysis), stratifying by dose level and overall. The number of ongoing participants will be included for outputs provided prior to the final analysis.

Listings will be provided for participant disposition, along with reasons for exclusion or discontinuation. An additional participant-level listing will be provided, indicating each observation period (Year) that he entered, and his duration in that period, along with his total study duration, as of the date of data cut (or conclusion date).

Potentially important protocol deviations (corresponding to those reported as 'Major') will be presented in a data listing.

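### The SAP gives two conflicting meanings of enrolled, and the Safety set hangs on that word: a dosed participant who breached eligibility is out under one meaning and in under the other

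*SAP*

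**What the plan says.** **SAP Section 4** is a three-row table. Enrolled is "All participants who sign the informed consent form (ICF) and meet all inclusion/exclusion criteria". Safety is "All participants enrolled in this study who receive any portion of study intervention". The third set, Evaluable, is also restricted to enrolled participants.

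**Protocol 9.3** defines Enrolled in the same way: "All participants who sign the ICF and meet all inclusion/exclusion criteria". Its Safety cell holds two sentences. The first requires enrolment, any portion of study drug and at least one post-baseline safety assessment. The second reads "All participants who enrolled in the study and received the study intervention".

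**SAP 6.5.2**, on disposition, gives another meaning: "Enrolled participants are those who have been screened, are not considered to be a screen failure, and who have been approved by the Medical Monitor". Protocol 5.4 supplies the missing term: "Screen failures are defined as participants who consent to participate in the clinical study but are not subsequently entered in the study".

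**SAP Section 1**, in the version 2 entry of the change history, records the aim of the revision: "The Safety population will be all participants who received study intervention". That is log text, so it shows intent and is not itself an operative definition.

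The Safety set carries the adverse event analyses (Protocol 9.4.1, SAP 6.6), FVIII activity (SAP 6.1.2), the annualized infusion rate (SAP 6.2.1) and the annualized bleeding rate (SAP 6.2.2).

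**The concern.** A safety population should depend on exposure alone. Here it depends on exposure plus a word that the SAP defines twice, and the definition nearest to hand, one row higher in the same table, turns on eligibility. A programmer who applies that table as written would drop a participant who was infused and later found not to have met a criterion. He would then be in no analysis set, since Evaluable carries the same enrolment condition and there is no all-treated set to fall back on.

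Both primary endpoints and the two main bleeding-related secondary endpoints use the set. The treatment is a single infusion that cannot be withdrawn, so a participant left out of the tables remains exposed. With about 20 participants, reported by dose level, one person is a visible part of every denominator.

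**Working it through.** The plan states no figure to reproduce. Protocol 9.2 says that the number of participants is not statistically derived, and SAP 5.1 says that the analyses are purely descriptive. The check is mainly one of logic.

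**Step 1. Classify one hypothetical participant.** He signed consent, was approved by the Medical Monitor and was infused. An eligibility breach came to light afterwards.

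| Source of the meaning of enrolled | Test | Enrolled? | In Safety? |
|---|---|---|---|
| SAP Section 4; Protocol 9.3 | consent and every criterion met | No | No |
| SAP 6.5.2 with Protocol 5.4 | screened, entered (so not a screen failure), approved | Yes | Yes |
| SAP Section 1, version 2 entry (intent only) | received study intervention | not used | Yes |

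Neither document says which meaning governs the Safety row. The conflict is therefore real, and one of the two operative readings departs from the recorded intent.

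**Step 2. Compare protocol and SAP.** The post-baseline-assessment condition survives in the first Safety sentence of Protocol 9.3. It is absent from SAP Section 4, and the SAP history records its removal. The protocol lets the SAP modify its outline (Protocol Section 9), so the analysis is settled on this point. The protocol sentence is a leftover.

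**Step 3. Size of one exclusion.** The planned number is about 20 (Protocol 9.2). The share removed is 1/20 = 5%. In a dose cohort of n participants it is 1/n, which is 1/2 if the cohort stays at the initial two (Protocol 4.1) and less if it is expanded.

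**Step 4. Illustration for scale.** Assume 20 dosed, one of them ineligible, and that he has the only occurrence of some event. Intervals are exact (Clopper-Pearson) at 95%.

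- All treated: 1/20 = 5.0% (0.1% to 24.9%).
- Section 4 read literally: 0/19 = 0% (0% to 17.6%).

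If he does not have the event, removing him pushes the incidence the other way. For one event among the other 19, 1/20 = 5.0% becomes 1/19 = 5.3%.

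**Step 5. How likely is it that the question arises?** The documents give no breach rate. If each dosed participant has probability p of a breach found only after dosing, independently, the chance of at least one among 20 is 1 − (1 − p)^20:

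| Assumed p | Chance of at least one |
|---|---|
| 1% | 18% |
| 2% | 33% |
| 5% | 64% |
| 10% | 88% |

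These values of p are assumptions chosen to show a range.

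**The case against.** The strongest reply is that no competent team would drop a treated participant here. The Safety row speaks of being enrolled in the study and does not cite the Enrolled set by name. Eligibility is confirmed before product is ordered (Protocol 6.2), and nothing in Section 4 says that it is judged again after dosing. SAP 6.5.2 and Protocol 5.4 keep the participant in, and the version history states the aim outright. Eligibility waivers are not permitted (Protocol Section 5). An exclusion would also show up: SAP 6.5.2 plans listings of reasons for exclusion and of potentially important protocol deviations, and the external monitoring committee reviews safety about every six months.

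Most of this stands. It makes exclusion uncertain and would make it detectable. It does not say which definition governs, and a listing does not correct a denominator in a summary table. A bar on waivers does not prevent a breach from being discovered after dosing.

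A reader might go further and infer that such a participant necessarily drops out of the primary safety analysis. The documents do not support that, because 6.5.2 offers an equally operative meaning that retains him. A reader might also infer that the wording biases safety and efficacy favourably. That is not shown either. Some criteria concern the liver, inhibitors or capsid antibodies, but others concern bleed counts, exposure days, contraception or recent participation in another study. The direction depends on the criterion breached and on what happened to that participant. A fall in cohort incidence from 1/2 to 0/1 can be constructed, but only by assuming a breach, a cohort that stays at two, and that he has its only event.

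**Conclusion.** Wrong as written, of minor severity. The SAP contains two definitions of enrolled that classify the same dosed participant differently, and the Safety set depends on which one is applied. The literal Section 4 reading, shared by Protocol 9.3, contradicts the recorded intent that Safety comprise all who received study intervention. The consequence is contingent on a breach among dosed participants, and none is reported. If one occurred and Section 4 were applied literally, about 5% of the overall denominator would be lost per participant, and more within his dose cohort, across the adverse event, FVIII activity, infusion rate and bleeding rate summaries. No direction of bias can be claimed in advance. The 5% rests on the planned number of about 20.

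**What to change.** 1. In SAP Section 4 and Protocol 9.3, define Safety as every participant who received any part of the study intervention, with no reference to enrolment.
2. In Protocol 9.3, delete the leftover sentence that requires a post-baseline safety assessment, so that the protocol matches the SAP and has one Safety definition.
3. Choose one definition of Enrolled and use it in SAP Section 4, SAP 6.5.2 and Protocol 9.3. Once Safety no longer depends on the term, either wording could serve.
4. Report any eligibility breach among dosed participants in the protocol deviation listing already planned in SAP 6.5.2.

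The cost is a few words in each document. No new data or analyses are needed, and if no dosed participant breached eligibility and all have post-baseline safety data, no reported figure changes because of the Safety wording.
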